Compliance This study will adhere to the conditions and principles outlined in the EU Directive 2001/20/EC, EU Directive 2005/28/EC and the ICH Harmonised Tripartite Guideline for Good Clinical Practice (CPMP/ICH/135/95). It will be conducted in compliance with the protocol, the UK Policy Framework for Health and Social Care Research, General Data Protection Regulation (GDPR) and Data Protection Act, 2018, Human Tissue Act 2004 and other regulatory requirements as appropriate.

**Funding** The ELDER trial is being funded by the Eklund Foundation for Odontological Research and Education, an organisation established to support international research and education in Dentistry.

This study is included in the NIHR CRN portfolio and therefore is supported by NIHR CRN North East and North Cumbria Network.

#### **Trial Documentation:**

# **Trial reporting**

ELDER Monthly record will be complemented by trial staff and copies should be emailed to the below trial specific email address:

[contact]

#### **Serious Adverse Events:**

# **SAR** reporting

SAEs will be reported by the RN on the ELDER Monthly Record

Where an adverse event meets the definition of a SAR the Clinical Trial Coordinator should be informed immediately, and a SAR form should be completed by the responsible person and emailed to the ELDER Trial email address (See section 10.5 for more details).

Email: [contact] [contact]

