# 10.5 Collecting and Reporting procedure

# 10.5.1 Adverse Events

Care home staff will report all events that meet the definition of an AE other than those events that do not require reporting (see section 10.6). The care home staff should manage those events excluded from reporting according to routine care home procedures. If an adverse event has occurred, the care home staff should inform the trial staff immediately or during the regular monthly data collection visit. The trial staff will collect and report the data directly into the CRF paper form specific for recording AEs (HRA/Non-CTIMP safety report to REC form) and into the ELDER Monthly Record.

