#### 10.5.2 Serious Adverse Events

All SAEs will be collected as part of a routine monthly follow-up (recorded by the trial staff on the ELDER Monthly Record under a separate subheading 'Further Comments – CRF Information' and into an SAE form (HRA/Non-CTIMP safety report to REC form) from the time of consent until the 9-month follow-up period). The delivery staff will discuss SAEs with a second delegated assessor (CTC from the coordinating centre) to confirm the causality classification (definitely, probably, possibly, unlikely, not related). The details of the second assessment will be reported on the ELDER Monthly Record under Further Comments – CRF Information. If the two assessors have assigned a different classification for an event assessed, then the highest category of causality (most likely to be related) will be selected, and the CI will confirm the assessment.

[figure not shown]

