#### 10.5.3 Serious Adverse Reaction

An SAE classified by the delivery staff/CTC and further confirmed by the CI as being probably or definitely related to the study product (diagnostic tests confirming septicaemia or the suspected pathogen is identified as the Bacillus strain used in the ELDER study product) will be classed as a SAR. In such cases, the trial staff should complete a purpose-designed SAR form, and the original

form returned to CTC within four days of the trial staff becoming aware of these events. The trial staff completing the report should include a detailed explanation of the event and supplement the report with clinical test results; if the hospital reports are not available at the time of reporting, the trial staff should forward the follow-up information as soon as possible to CTC, who would include these additional data in the appropriate report. Related and unexpected SAEs (i.e., all unexpected SARs) will be reported to the REC within 15 days of the CI/CTC becoming aware of the event. The CTC is responsible for additionally reporting SARs to the monitoring committee and the study product manufacturer (SACCO Systems) as appropriate.

Contact details for reporting SARs
Please Email to [contact], attention Clinical Trial Coordinator
Queries
[contact] (Mon to Fri 09.00 – 17.00)

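### SAR deadlines run from awareness, but the visible text lets care homes hold a serious event until the monthly visit, so awareness may lag the event by weeks

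*Protocol*

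**What the plan says.** The front-matter page on SAR reporting sets two routes. For SAEs it says "SAEs will be reported by the RN on the ELDER Monthly Record". For an event that meets the SAR definition it says "the Clinical Trial Coordinator should be informed immediately", and it refers the reader to section 10.5.

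Section 10.5.1 governs the step from care home to trial team. If an adverse event occurs, "the care home staff should inform the trial staff immediately or during the regular monthly data collection visit". No separate rule is given for serious events.

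Section 10.5.2 says "All SAEs will be collected as part of a routine monthly follow-up". On causality it says "The delivery staff will discuss SAEs with a second delegated assessor (CTC from the coordinating centre) to confirm the causality classification", and the chief investigator (CI) confirms the assessment.

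Section 10.5.3 defines a SAR as "An SAE classified by the delivery staff/CTC and further confirmed by the CI as being probably or definitely related to the study product". It wants the SAR "form returned to CTC within four days of the trial staff becoming aware of these events". Related and unexpected SAEs "will be reported to the REC within 15 days of the CI/CTC becoming aware of the event".

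The abbreviations list expands SAR as Serious Adverse Event, the same words as for SAE. Section 10.1 uses SAR for Serious Adverse Reaction.

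**The concern.** The people who see an event first are the care home staff. The protocol's note on terms uses trial staff for the trial team, and care home staff are named separately throughout. The deadlines in section 10.5.3 therefore bind people who may not yet know of the event, while the only timing rule on those who do know offers the monthly visit as an equal alternative to immediate notice.

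The stake is participant safety. Section 10.5.3 illustrates a SAR with confirmed septicaemia or identification of the product strain as the pathogen. Homes are randomised as clusters (section 6.4) with up to fifteen participants each (section 4), so other participants in the home are allocated the same product while the event is unreported. The emergency meeting and urgent advice that section 15.5 offers through the data monitoring committee (DMC) cannot start until the trial team has been told. Whether anything should then change for those residents is a clinical matter outside this point; the issue is when anyone in the trial can first consider it.

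**Working it through.** The plan gives no figure for the time from event to report, so there is none to reproduce. The check takes each rule, asks what starts its clock, and adds the intervals.

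**What starts each clock**

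| Step | Time allowed | Clock starts at |
|---|---|---|
| Care home to trial staff (10.5.1) | At once, or next monthly visit | Event |
| SAE collection (front matter, 10.5.2) | Monthly | Routine visit |
| Notice of SAR to coordinator (front matter) | Immediately | Event meeting the SAR definition |
| SAR form to coordinator (10.5.3) | 4 days | Trial staff awareness |
| Report to REC (10.5.3) | 15 days | CI or coordinator awareness |

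Only the first step is tied to the event, and it carries the monthly option.

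**Illustrative delays.** Assumptions: a month of 31 days, an event just after one visit, the optional immediate route not used, and the coordinator told on the day trial staff learn of the event.

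- Event to trial staff awareness: up to about 31 days.
- Event to SAR form: 31 + 4 = 35 days.
- Event to REC: 31 + 15 = 46 days. The form's four days run alongside the 15 and are not added to them.

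**With the site visits of section 13.1.** Trial staff visit each home two or three times a month. If the visits are evenly spaced (assumed) and serious events are picked up at them:

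- Awareness: 31 / 3 ≈ 10 days to 31 / 2 ≈ 16 days.
- SAR form: 10 + 4 = 14 to 16 + 4 = 20 days.
- REC: 10 + 15 = 25 to 16 + 15 = 31 days.

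**What triggers the immediate notice.** Under sections 10.5.2 and 10.5.3 an SAE becomes a SAR only after the delivery staff and the coordinator have classified it and the CI has confirmed. The coordinator is the second assessor, so by the time an event has SAR status the coordinator already knows of it, and read strictly the immediate notice adds nothing. Read with the abbreviations list, the front-matter rule would instead require immediate notice of every SAE, which does not fit the monthly rule on the same page or in section 10.5.2. Neither reading gives a usable starting point.

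**The case against.** A reader might infer that the immediate and four-day rules cannot work as written. The text does not support that. The four-day rule runs from trial staff awareness and can be met whenever the event surfaces. The immediate rule applies once the SAR definition is met and can also be met. Nor do the two conflict: one is a notice, the other a completed form with an explanation and test results.

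A reader might also add all three intervals, 31 + 4 + 15 = 50 days to the REC, and call that the worst case under the rules. That sum needs the coordinator to learn of the event first from the SAR form, contrary to the front-matter notice and to the coordinator's role as second assessor. Even 46 days is not a strict bound, because no time limit is given for the discussion between delivery staff and coordinator.

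There is real mitigation. Section 10.5.1 allows immediate notice, and nothing in section 10.5.2 forbids it. Section 10.4 relies on care home staff to spot deterioration very early and has them told of the pre-specified events. Section 13.1 puts trial staff on site more than once a month. Section 15.5 provides for urgent contact with the DMC. The SAE reporting flowchart is not visible in the text reviewed and may contain timings, so its content cannot be counted as missing.

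This removes any claim of unworkable rules and makes a month an outer figure, not a typical one. It does not remove the core. Early recognition by care home staff is not a duty to pass the event on. Section 13.1 describes checks of performance, GCP compliance and records, not SAE collection. Whatever the flowchart shows, the choice between immediate and monthly notice in section 10.5.1 would have to be reconciled with it.

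**Conclusion.** The point holds in this form: the SAR deadlines count from awareness, and the visible text does not oblige care homes to make the trial team aware of a serious event promptly. With every visible rule met, awareness may lag the event by up to about a month, illustratively 35 days to the SAR form and 46 days to the REC, or about 14 to 20 and 25 to 31 days if the site visits pick events up. These figures rest on a 31-day month, no use of the immediate route and same-day notice to the coordinator; the shorter ones also assume evenly spaced visits. They show what the wording permits, not what would usually happen.

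The trigger for immediate notice is a second, related ambiguity. Both should be amended: the possible harm is to participants and the change is small.

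**What to change.** Reconcile the front-matter reporting page, the abbreviations list, sections 10.5.1 to 10.5.3 and the SAE flowchart:

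- Have care home staff notify the trial team of any reportable SAE, meaning one outside the section 10.6 exclusions, as soon as they become aware of it. Remove the monthly option for serious events. Limiting the duty to reportable events respects the aim in section 10.4 of not burying safety signals in unrelated data.
- Keep the ELDER Monthly Record as a completeness check on SAEs already notified.
- Start the immediate notice to the coordinator when a SAR is suspected, not after classification and confirmation. The four-day form and 15-day REC rules can stay as separate later steps.
- Correct the expansion of SAR in the abbreviations list.

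The cost is a text amendment, one line in the existing 15-minute care home training (section 7) and some additional calls. How many calls cannot be judged from the protocol: hospitalisation counts as an SAE in a frail population, and the section 10.6 list removes some of those events but not all.

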# **Abbreviations**

| Term   | Description  |
|--------|--|
| AE     | Adverse Event  |
| AR     | Adverse Reaction                                       |
| СН     | Care Home  |
| CHR    | Care Home Resident(s)                                  |
| CI     | Chief Investigator                                     |
| CRF    | Case Report Form                                       |
| CRN    | Clinical Research Network                              |
| CTC    | Clinical Trials Coordinator                            |
| CTIMP  | Clinical Trial of an Investigational Medicinal Product |
| CQC    | Care Quality Commission                                |
| DDT    | Direct Delivery Team                                   |
| DMC    | Data Monitoring Committee                              |
| ENRICH | EmbeddiNg Research In Care Homes                       |
| GCP    | Good Clinical Practise                                 |
| ICF    | Informed Consent Form                                  |
| MAR    | Medication Administration Record                       |
| MUST   | Managing Undernutrition South Tees                     |
| NIHR   | National Institute of Health Research                  |
| PCT    | Primary Care Team                                      |
| PI     | Principle Investigator                                 |
| PIS    | Participant Information Sheet                          |
| PPI    | Patient and Public Involvement                         |
| PRCL   | Primary Root Caries Lesion                             |
| RCT    | Randomised Control Trial                               |
| REC    | Research Ethics Committee                              |
| RN     | Research Nurse   |
| SAE    | Serious Adverse Event                                  |
| SAR    | Serious Adverse Event                                  |
| SIV    | Site Initiation Visit                                  |

| TMF | Trial Master File      |
|-----|------------------------|
| TSC | Trial Site Coordinator |

‡NB The terms will be used interchangeably throughout the document: Wherever the term clinical study is used, it shall be referred to as 'trial' or 'study'; similarly, the reference to Teesside University is used herein as 'coordinating centre' or 'sponsor organisation'; likewise, the reference to the trial team is used therein as 'trial staff' or 'research member'.

# TRIAL SUMMARY

[figure not shown]
| Title                | Improving the oral health of older adults using milk supplemented with fluoride and probiotics: An interventional feasibility study and pilot RCT   |
|----------------------|---|
| Acronym              | ELDER   |
| Short title          | ELDER   |
| Trial configuration  | Multi-centre, open-label, parallel-group, four-arm, prospective, cluster-randomised, placebo-controlled feasibility trial   |
| Trial setting        | Care homes in TeesValley (residential, nursing, mixed)  |
| Planned sample size  | 240 participants  |
| Eligibility criteria | 
 
Care Home (cluster level) criteria:         Inclusions         
 
Site: Tees Valley care homes for older people, with, without nursing or mixed
 
Size: ≥ 5 resident beds in the care home in total with mental capacity
 
 
 
Exclusions
 
 |
|                      | 
 
Care homes not located within the Tees Valley region
 
Care homes with inadequate resident capacity where there are < 5 beds in total
 
   |
|                      | Care Home Resident criteria at trial entry:   |
|                      | 
 
Inclusions
 
Full-time resident in a care home
 
Age ≥ 65 years
 
   |

|  | No acute or immunocompromised medical   |
|--|---|
|  | condition   |
|  | Able to give informed consent for participation   |
|  | Tolerance for dairy products  |
|  |   |
|  | Exclusions  |
|  | Residents who are receiving planned respite or end-   |
|  | of-life or palliative care  |
|  | • Residents who are < 65 years of age   |
|  | Residents with any immunocompromised medical conditions   |
|  | Residents who lack the mental capacity to provide   |
|  | informed consent  |
|  | Residents who are currently taking/being prescribed   |
|  | regular probiotics  |
|  | Residents with severe lactose intolerance   |
|  | Residents who do not have a working level of oral   |
|  | English   |
| Follow-up duration                     | The recruitment window will be open for three months from the official trial start date, and the follow-up schedule will begin from the time the participant gives written informed consent and would from then depend on the length of time the participant remains active in the trial.   |
|  | rengar of time the participant femalis active in the than.  |
|  | Participants will have a baseline assessment and endpoint assessment after nine months.   |
| Planned trial period                   | Participants will have a baseline assessment and endpoint   |
| Planned trial period  Trial Objectives | Participants will have a baseline assessment and endpoint assessment after nine months.  The participants to drink milk supplemented with fluoride or probiotics or a placebo for nine months or until 30/12/23, whichever is sooner.  1. To evaluate the effect of milk supplemented with probiotics and/or fluoride on primary root caries lesions (PRCL)   |
| _                                      | Participants will have a baseline assessment and endpoint assessment after nine months.  The participants to drink milk supplemented with fluoride or probiotics or a placebo for nine months or until 30/12/23, whichever is sooner.  1. To evaluate the effect of milk supplemented with probiotics and/or fluoride on primary root caries lesions (PRCL)  2. To record rates of recruitment, retention, and  |
| _                                      | Participants will have a baseline assessment and endpoint assessment after nine months.  The participants to drink milk supplemented with fluoride or probiotics or a placebo for nine months or until 30/12/23, whichever is sooner.  1. To evaluate the effect of milk supplemented with probiotics and/or fluoride on primary root caries lesions (PRCL)  2. To record rates of recruitment, retention, and completion.  |
| _                                      | Participants will have a baseline assessment and endpoint assessment after nine months.  The participants to drink milk supplemented with fluoride or probiotics or a placebo for nine months or until 30/12/23, whichever is sooner.  1. To evaluate the effect of milk supplemented with probiotics and/or fluoride on primary root caries lesions (PRCL)  2. To record rates of recruitment, retention, and completion.  3. To estimate variability for the potential outcome  |
| _                                      | Participants will have a baseline assessment and endpoint assessment after nine months.  The participants to drink milk supplemented with fluoride or probiotics or a placebo for nine months or until 30/12/23, whichever is sooner.  1. To evaluate the effect of milk supplemented with probiotics and/or fluoride on primary root caries lesions (PRCL)  2. To record rates of recruitment, retention, and completion.  3. To estimate variability for the potential outcome measures to inform sample size planning for a                  |
| _                                      | Participants will have a baseline assessment and endpoint assessment after nine months.  The participants to drink milk supplemented with fluoride or probiotics or a placebo for nine months or until 30/12/23, whichever is sooner.  1. To evaluate the effect of milk supplemented with probiotics and/or fluoride on primary root caries lesions (PRCL)  2. To record rates of recruitment, retention, and completion.  3. To estimate variability for the potential outcome  |
| _                                      | Participants will have a baseline assessment and endpoint assessment after nine months.  The participants to drink milk supplemented with fluoride or probiotics or a placebo for nine months or until 30/12/23, whichever is sooner.  1. To evaluate the effect of milk supplemented with probiotics and/or fluoride on primary root caries lesions (PRCL)  2. To record rates of recruitment, retention, and completion.  3. To estimate variability for the potential outcome measures to inform sample size planning for a                  |
| Trial Objectives                       | Participants will have a baseline assessment and endpoint assessment after nine months.  The participants to drink milk supplemented with fluoride or probiotics or a placebo for nine months or until 30/12/23, whichever is sooner.  1. To evaluate the effect of milk supplemented with probiotics and/or fluoride on primary root caries lesions (PRCL)  2. To record rates of recruitment, retention, and completion.  3. To estimate variability for the potential outcome measures to inform sample size planning for a definitive trial |

[figure not shown]
|                                    | 2 Detential aliminal dantal magnitus of the intervention  |
|------------------------------------|---|
|                                    | 2. Potential clinical dental results of the intervention, |
|                                    | including root caries and gingival inflammation           |
|                                    | 3. Bacterial counts in saliva and plaque at baseline      |
|                                    | and over a subsequent 9-month period                      |
|                                    | Secondary Endpoint:                                       |
|                                    | 1. Frequencies of infection                               |
|                                    | 2. Use of antibiotics and unscheduled pain killers        |
|                                    | 3. Urgent care appointments (medical/dental) over the     |
|                                    | 9-month period of intervention                            |
|                                    |   |
| Description of Intervention | This intervention will include:                           |
| -                                  | Administration of the study product once daily for five   |
|                                    | days a week – milk supplemented with probiotics and/or    |
|                                    | fluoride or matching placebo for nine months or until     |
|                                    | 30/12/23, whichever is sooner                             |
|                                    |   |

# **WORK FLOW DIAGRAM**

[figure not shown]
# Recruitment

[figure not shown]
# Intervention

# **Data Collection**

# Data Analysis

[figure not shown]

Saliva (Whole &/or oral swab) &/or Supragingival Plaque

#### PARTICIPANT FLOW DIAGRAM

\*Care home staff, or managers did not respond to calls or emails/were too busy

#### 1. INTRODUCTION

#### 1.1 Background

Globally, ageing populations present significant public health implications, with non-communicable diseases (NCDs) becoming the leading causes of disability and mortality. Oral diseases are among the most common and preventable NCDs, resulting in inadequate nutritional intake, deteriorating quality of life, and the subsequent impact on longevity (1).

Data from extensive cohort studies on the oral health of older adults (2) depicts a worrying situation, with dental caries (tooth decay) persisting as a significant problem. The National Institute for Health and Care Excellence (NICE) guidance on oral health identified dental caries as a significant problem, particularly among older people in the UK (3).

The James Lind Alliance Priority Setting Partnership (4) listed "prevention of tooth decay & reducing oral health inequalities at a community level" and "better oral care for the prevention/management of health conditions (e.g. malnutrition/chest infection)" among their top 10 "Oral and Dental Health" priorities.

A NICE research recommendation is to explore "community-based interventions, which are effective and cost-effective in improving oral health and reducing oral health inequalities among groups of adults at high risk of poor oral health", including interventions to increase fluoride exposure (3).

Although fluoride remains the most effective and economic protective agent against dental caries, its effectiveness is boosted when combined with other anti-caries agents such as probiotics offering general health as well as cost-saving benefits (5).

Cow's milk is a nutritious drink, providing a good source of protein and micronutrients and contributing to optimal hydration (6). Due to its low potential for caries generation, milk has been recommended as a convenient and cost-effective vehicle for delivering fluoride to older people residing in the community (7).

Providing milk supplemented with fluoride and/or probiotics (S-milk) could offer a potentially cost-effective method for caries prevention in older adults, particularly those living in care homes.

